133 To investigate the efficacy of liraglutide compared to placebo in reducing visceral adiposity
134 measured by MRI in overweight or obese subjects at high risk for cardiovascular disease after
135 40 weeks on-treatment.

136

137 **Secondary Objectives:**

138 To compare liraglutide and placebo regarding the effect on:

- 139 • Changes in abdominal subcutaneous adipose tissue by MRI
- 140 • Changes in total fat mass by MRI
- 141 • Changes in fat-free mass by MRI
- 142 • Changes in lower body adipose tissue mass by MRI
- 143 • Changes in hepatic fat content by MRI
- 144 • Changes in circulating blood biomarkers of cardiometabolic risk including markers of insulin
145 resistance, inflammation, lipids, and natriuretic peptides.

146

147 **Trial Design:**

148 This is a randomized, double-blind, parallel-group, placebo controlled, prospective clinical trial to
 149 be conducted at a single center over 46 weeks (40 weeks on-treatment). There are two
 150 treatment arms. Patients will be randomized to liraglutide 3.0 administered once a day by
 151 subcutaneous injection or matching placebo, in addition to a reduced-calorie diet and increased
 152 physical activity. All participants will be prescribed a 500 kcal per day deficit diet, based on
 153 estimated 24-h energy expenditure.¹ All participants will be instructed to maintain physical
 154 activity at the recommended level of 150 minutes of moderate activity per week.

155

156 Trial Population:

157 Planned number of subjects to be screened: 356 (2:1 screen to randomization ratio)

158 Planned number of subjects to be treated in run-in period: 214

159 Planned number of subjects to be randomized/started on trial medication(s):178

160 Anticipated number of subjects to be studied: At least 128 completers

161 Number of trial sites: Single center

162

163 Sample Size:

164 This trial is powered to detect a clinically meaningful difference in the percent relative reduction
 165 in VAT. The estimates used in the sample size calculations below are derived from prior data
 166 from the SCALE program. Assuming a mean 8% relative reduction of VAT among placebo
 167 treated subjects and an expected 16% relative reduction of VAT among liraglutide treated
 168 subjects (with a standard deviation of 16%, based on data from [²]), we expect to require 128
 169 total subjects (in a 1:1 trial drug:placebo randomization scheme) to achieve 80% power to

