401 causes thyroid C-cell tumors, including medullary thyroid carcinoma (MTC), in humans, as
402 human relevance could not be ruled out by clinical or nonclinical studies. Liraglutide is
403 contraindicated in patients with a personal or family history of MTC and in patients with Multiple
404 Endocrine Neoplasia syndrome type 2 (MEN 2). Based on the findings in rodents, monitoring
405 with serum calcitonin or thyroid ultrasound was performed during clinical trials, but this may

406 have increased the number of unnecessary thyroid surgeries. It is unknown whether monitoring
407 with serum calcitonin or thyroid ultrasound will mitigate human risk of thyroid C-cell tumors.
408

409 *Liraglutide and Body Composition*

410 Body composition was measured in a sub-study of Trial 1807 which included 113 patients (92
411 completers) from 7 European centers using dual energy x-ray absorptiometry (DXA) and
412 computerized axial tomography (CT) scans. Trial 1807² was a placebo-controlled 20 week trial
413 with open label orlistat, placebo and once daily injection of liraglutide. At 1 year liraglutide 3.0
414 mg recipients lost 5.8 kg (95% CI 3.7–8.0) more body weight than those on placebo and 3.8 kg
415 (1.6–6.0) more than those on orlistat (P<0.0001). In this body composition sub-study at week
416 20, mean total body fat mass was reduced between 5.0-6.9 kg with liraglutide, 4.4 kg with
417 placebo and 4.9 with orlistat. The percentage of body weight lost due to fat was 80-90% of the
418 total weight lost in the liraglutide treated group and 63% in the placebo group. The weight loss
419 and reduction in waist circumference with liraglutide was primarily due to reduction in fat mass
420 rather than lean body mass. This sub-study also quantified the VAT and abdominal SAT mass
421 lost. Summary data from this body composition sub-study are presented in Table 1 and Figure 1
422 below:

423

424 While there was a numerical trend for greater VAT mass loss in the liraglutide 3.0 mg group, this
425 study was underpowered to detect between group differences in absolute or relative VAT mean
426 mass lost. This initial work is a fundamental first step but has important limitations, including: 1)
427 lack of study subjects in the United States; patients enrolled in this study were exclusively
428 recruited from European centers including Belgium, Czech Republic, Denmark, Finland,
429 Netherlands, Spain, and Sweden; 2) there were very few subjects treated with 3.0 mg of

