430 liraglutide (N=15); therefore this study was not only underpowered to detect clinically meaningful
431 differences in abdominal fat distribution, but also systematically underdosed; 3) the use of
432 ionizing radiation (with CT scans) limits the generalizability to other research projects that will
433 likely be conducted over long-term follow-up with repeat imaging; and 4) this study did not
434 directly quantify hepatic fat, a known correlate of insulin resistance and cardiometabolic risk.
435 We will address these limitations in the research proposed below.

436

[figure not shown]
437 Table 1. Body composition assessed by DXA and CT in a subgroup of participants at 20 weeks

Placebo n = 14	Liraglutide				Orlistat n = 12
	1.2 mg n = 15	1.8 mg n = 13	2.4 mg n = 15	3.0 mg n = 15	
Dual-energy X-ray absorptiometry measurements: body composition at randomization (kg)^a					
Fat tissue	45.8 (10.5)	43.5 (7.6)	45.0 (8.8)	42.6 (6.1)	43.9 (8.4)
Lean tissue	51.0 (11.0)	55.0 (8.9)	51.7 (11.3)	50.6 (11.9)	53.1 (10.3)
Relative change at week 20 (%)					
Fat tissue ^b	-11.9 (2.5)	-13.9 (2.7)	-13.0 (2.6)	-16.5 (2.5)	-15.4 (2.6)
Change vs placebo ^c	—	-2.0 (-8.9 to 4.9); P = 0.57	-1.1 (-8.0 to 5.9); P = 0.76	-4.6 (-11.2 to 2.1); P = 0.18	-3.5 (-10.3 to 3.4); P = 0.32
Lean tissue ^b	-1.3 (1.0)	-0.9 (1.1)	-2.9 (1.1)	-2.6 (1.0)	-2.0 (1.1)
Change vs placebo ^c	—	0.4 (-2.4 to 3.3); P = 0.77	-1.6 (-4.4 to 1.3); P = 0.28	-1.3 (-4.1 to 1.4); P = 0.33	-0.7 (-3.6 to 2.1); P = 0.61
Computerized axial tomography measurements: body composition at randomization (cm²)^a					
Visceral fat	136 (38)	172 (77)	121 (39)	149 (76)	145 (69)
Subcutaneous fat	474 (107)	453 (68)	476 (71)	426 (75)	434 (116)
Relative change at week 20 (%)					
Visceral fat ^b	-13.8 (5.7)	-19.0 (6.3)	-19.4 (6.0)	-23.0 (5.7)	-20.3 (6.0)
Change vs placebo ^c	—	-5.1 (-21.2 to 11.0); P = 0.53	-5.6 (-21.8 to 10.6); P = 0.49	-9.2 (-24.7 to 6.4); P = 0.25	-6.4 (-22.1 to 9.2); P = 0.42
Subcutaneous fat ^b	-12.1 (3.0)	-15.6 (3.3)	-15.9 (3.6)	-19.3 (3.0)	-15.3 (3.3)
Change vs placebo ^c	—	-3.5 (-11.8 to 4.9); P = 0.41	-3.8 (-12.6 to 5.1); P = 0.40	-7.1 (-15.2 to 1.0); P = 0.09	-3.1 (-11.5 to 5.2); P = 0.45

^aMean (s.d.). ^bEstimated mean (s.e.). ^cEstimated mean (95% CI); P-value. Values are for participants who completed the substudy according to the protocol (PP completers).

438
439
440

Figure 1. Relative changes in Visceral and Abdominal Subcutaneous Fat Mass Assessed by CT

441
442
443

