631 **Imaging Assessments**

632 The primary and secondary endpoints of visceral fat, abdominal subcutaneous fat, lower body
 633 fat, liver fat, and total body fat and fat-free (lean) mass will be assessed using a Phillips 3T MRI
 634 system utilizing a two point Dixon fat-water segmentation technique (Advanced MR Analytics,
 635 Sweden).²¹ This MRI system has been extensively studied and validated in multiple cohorts,²¹⁻²³
 636 has excellent test/retest precision and reliability,²⁴ and is rapid (<6 minutes) and therefore cost
 637 effective.

638 **STATISTICAL CONSIDERATIONS:**

641 **Sample Size Calculation:**

642 This trial is powered to detect a clinically meaningful difference in the placebo-corrected relative
 643 reduction in VAT. The estimates used in the sample size calculations below are derived from

644 prior data from the SCALE program. Assuming a mean 8% relative reduction of VAT among
 645 placebo treated subjects and an expected 16% relative reduction of VAT among liraglutide
 646 treated subjects (with a standard deviation of 16%, based on data from [2]), we expect to require
 647 128 total subjects (in a 1:1 trial drug:placebo randomization scheme) to achieve 80% power to
 648 detect an 8% difference between groups at an alpha level of 0.05. Assuming an estimated 28%
 649 of subjects may withdraw trial medication during the trial, we expect a planned total of 178
 650 patients will be randomized in order to achieve at least 128 completers of the full trial protocol.
 651

Placebo-corrected Effect Size	Power		
	80%	85%	90%
Sample Size (Total N, 1:1 randomization)			
5%	322	368	432
8%	128	146	170
10%	82	92	108

652
 653 **Statistical Methods:** A formal statistical analysis plan will follow. Briefly, baseline
 654 characteristics between liraglutide and placebo treated groups will be compared using
 655 appropriate parametric or non-parametric tests depending on the distribution of the data. The
 656 primary outcome will be analyzed using an intention to treat analysis. Mean change in outcome
 657 measurements will be compared between groups using the appropriate statistical test.
 658 Outcomes will also be analyzed by subgroups including age (above/below median), sex, race
 659 (non-Hispanic black, non-Hispanic white, and Hispanic), BMI category (overweight, class I
 660 obese, class II/III obese), and prediabetes status (yes/no). In order to minimize type II error in

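### The planning SD of 16% for percent VAT change is credited to reference 2, but the data the protocol shows from that trial imply about 21%, and the 80% power has no margin for a larger SD

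*Protocol*

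**What the plan says.** The Sample Size paragraph of the synopsis and the Sample Size Calculation under Statistical Considerations give the same inputs: mean VAT reductions of 8% on placebo and 16% on liraglutide, 1:1 allocation, alpha 0.05 and 80% power. This leads to 128 completers and, at 28% withdrawal, 178 randomized. Statistical Methods makes all tests two-sided. Both paragraphs open by saying that the estimates derive from the SCALE program. Both then give the SD its own source, reference 2: "with a standard deviation of 16%, based on data from [2"].

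The section Liraglutide and Body Composition attaches mark 2 to Trial 1807: "Trial 1807² was a placebo-controlled 20 week trial". It says that the sub-study is summarised in Table 1 and Figure 1, and concedes that this "study was underpowered to detect between group differences in absolute or relative VAT mean" mass lost. The Table 1 footnote reads: "Values are for participants who completed the substudy according to the protocol (PP completers"). Table 1 reports relative change in visceral fat at week 20 as estimated means with standard errors, and contrasts with placebo with 95% confidence intervals.

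**The concern.** No SD of 16% for VAT change appears in the text or in the legible part of Table 1, and no derivation is given. The intervals in Table 1 look too wide for 16% at the printed arm sizes.

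The stated 80% power is what justifies 128 completers and 178 randomized. The sample-size table varies the effect and the power but holds the SD at 16% throughout, so a reader cannot see how much depends on it. If the SD is really nearer 21%, the power is overstated and a null result could be misread as absence of effect. Type I error and the validity of the analysis are not touched.

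**Working it through.** **1. The plan's own figure.** For two independent means, n per arm = 2(1.960 + 0.842)² × 16² / 8² = 62.8, so 63 per arm and 126 in total by the normal approximation. The t-test gives 64 per arm, 128 in total, with power 80.1%. Then 128 / (1 − 0.28) = 177.8, so 178. The other cells of the sample-size table reproduce at SD 16 to within about 2 patients.

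**2. SD implied by Table 1.** For each visceral-fat contrast with placebo, SD = half-width / t(0.975) / √(1/14 + 1/n), with placebo n = 14. Columns are read left to right. The pooled df are 84 printed patients less 6 arms = 78.

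| 95% CI | Half-width | n | SD, two-arm df (25 or 27) | SD, 78 df |
|---|---|---|---|---|
| −21.2 to 11.0 | 16.10 | 15 | 21.1 | 21.8 |
| −21.8 to 10.6 | 16.20 | 13 | 20.4 | 21.1 |
| −24.7 to 6.4 | 15.55 | 15 | 20.4 | 21.0 |
| −22.1 to 9.2 | 15.65 | 15 | 20.5 | 21.2 |

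Example, first row on 27 df: 16.10 / 2.052 / 0.3716 = 21.1. The placebo standard error gives a similar value, 5.7 × √14 = 21.3, but it is only secondary because the arm standard errors look model-based.

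**3. Does the broken table matter?** Table 1 has six arm headings over five legible values. Pairing any of the four intervals with any printed arm size (12, 13 or 15) against 14 gives 19.2 to 21.9. At SD 16 with 14 against 15 patients, the expected half-width is 11.8 to 12.2, not about 16.

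**4. Sampling error.** 95% limits are SD × √(df / χ²).

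- SD 21 on 78 df: 18.2 to 24.9.
- SD 20.5 on 27 df: 16.2 to 27.9.
- SD 20.4 on 25 df: 16.0 to 28.2.

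The four contrasts share one placebo arm, so their agreement is not four independent confirmations.

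**5. Power for 8 points** (two-sided 5%, noncentral t):

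| Analysed | SD 16 | SD 18 | SD 21 | SD 25 | SD 28 | Largest SD keeping 80% |
|---|---|---|---|---|---|---|
| 128 | 80% | 70% | 57% | 44% | 36% | 16.0 |
| 150 | 86% | 77% | 64% | 50% | 41% | 17.4 |
| 178, no dilution | 91% | 84% | 71% | 57% | 47% | 18.9 |

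The difference detectable with 80% power at SDs of 18, 21 and 25 is 9.0, 10.5 and 12.5 points with 128 analysed, and 7.6, 8.9 and 10.6 points with 178.

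**6. The planned means.** Table 1 shows a 13.8% reduction on placebo and, read left to right, 20.3% on 3.0 mg, with a contrast of 6.4 points. The plan uses 8%, 16% and 8 points. The means therefore do not come straight from Table 1 either.

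**The case against.** The best case for the plan is that Table 1 may never have been the planning dataset. The protocol says the SD rests on reference 2, not on Table 1, and it credits the estimates as a whole to the SCALE program. The planned means differ from Table 1 as well. The reference entry and Figure 1 are not visible, and an SD of 16% reported elsewhere in that source would settle the matter. This stands: the documents show a mismatch between a figure and the data shown for its cited source, and do not prove that 16% is false.

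Second, 21% is not an observed SD. It is back-calculated from intervals that probably come from a covariate-adjusted model. Under a common-variance model, covariate imbalance can widen a contrast, so the residual SD could be somewhat below the value derived here. This also stands. However, adjustment usually makes the residual SD smaller than the raw SD, and the plan's calculation is a plain comparison of two means. Model-based estimation therefore does not obviously explain a lower planning value.

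Third, Table 1 covers CT at 20 weeks in per-protocol completers of a small study. This trial uses MRI at 40 weeks in a population enriched for visceral fat. The protocol does say that enrichment should improve power and that the MRI method is precise, and a smaller SD is conceivable. It ties neither statement to 16%.

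Fourth, 128 may be the pessimistic count. Subject Replacement and Visit Procedures ask withdrawn patients back at week 40, and the intention-to-treat analysis includes them. This is why the range up to 178 is shown. Those patients would have stopped treatment, however, so an undiluted 8-point effect is the optimistic end.

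**Conclusion.** The concern holds as a mismatch between the planning SD and the data shown for its cited source. At the Table 1 value of 21%, power falls short of 80% whether 128 (57%) or all 178 (71%) are analysed. At SD 18, the lower end of the pooled range, 178 would still suffice (84%). With 128 analysed, any SD above 16.0% loses the stated power.

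A reader might infer that the trial's true power is 57%, or that the calculation is wrong. The documents support neither. The arithmetic is sound, 57% is the low-count case at one back-calculated SD, and on two-arm degrees of freedom 16% is at the very edge of what Table 1 allows. A faulty or incomplete citation would explain the discrepancy as well as a faulty SD would.

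The conclusion assumes that mark 2 means the same source in both places, that the contrast intervals are conventional t-based intervals on about the printed arm sizes, and that the 18 to 25 range uses variance pooled over six arms, which the protocol does not state.

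**What to change.** In both sample-size paragraphs, reconcile the SD with its cited source. If a source does support 16%, whether other SCALE data or a part of reference 2 not shown in Table 1, cite it, show how the value was obtained, and say why Table 1 does not apply.

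Otherwise, restate the power or the detectable difference, and the sample-size table, over SDs of 16% to 25% with 21% marked as the Table 1 value, for 128 to 178 analysed. The figures in the working can be used directly.

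The cost is a rewording of two paragraphs and one table, and possibly a less favourable stated power. No extra patients or procedures are needed.

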371 their baseline body weight and approximately 30% lost greater than 10% of their body weight.
372 These changes were significantly greater than weight loss seen in the placebo arms of these
373 three trials. In study 3 there were a statistically greater number of patients randomized to
374 placebo that gained at least 0.5% of their body weight at week 56. Liraglutide use was also
375 associated with a reduction in waist circumference, blood pressure and modest reductions in
376 total cholesterol, LDL and increase in HDL. Liraglutide was associated with an increase in heart
377 rate of approximately 2 beats per minute.

378
379 *Tolerability and Adverse Events*

380 Treatment with liraglutide in prior obesity trials was generally well tolerated. Approximately 70%
381 of patients randomized to liraglutide completed the trials on medication. The withdrawal rate
382 was approximately 8.5% in the liraglutide arms and 8.6% in the placebo treated patients.
383 Serious adverse events were relatively uncommon, but were more frequent in liraglutide-treated
384 subjects compared with placebo (4.2 vs. 2.4%). GI side effects seen in the SCALE
385 Maintenance trial were common in patients taking liraglutide 3.0 mg. The frequency of nausea
386 was 47.6%, of diarrhea was 17.9%, of constipation was 26.9% and of vomiting was 16.5%.
387 Other less common AEs included dyspepsia (9.4%), abdominal pain (6.6%), abdominal
388 distension (6.1%), eructation (5.2%), and flatulence (5.2%).²⁰

389
390 There have been rare, spontaneous post-marketing reports of acute pancreatitis in patients
391 without a history of pancreatitis being treated with liraglutide. In the obesity clinical trials, acute
392 pancreatitis was confirmed in 9 of 3291 liraglutide treated patients and 1 of 1843 placebo
393 treated patients. There were 3 additional cases of pancreatitis occurring in liraglutide treated
394 patients ranging 14 to 124 days after study discontinuation. A history of pancreatitis was an
395 exclusion criterion in clinical trials performed to date. If the investigator suspects acute
396 pancreatitis, all suspected drugs should be discontinued until confirmatory tests have been
397 conducted and appropriate treatment initiated.

398
399 Liraglutide causes dose-dependent and treatment-duration-dependent thyroid C-cell tumors at
400 clinically relevant exposures in both genders of rats and mice. It is unknown whether liraglutide

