482 **Primary Endpoint:**

- 483 • The liraglutide treatment effect on relative percent change from baseline in visceral adipose
484 tissue mass measured by MRI.

485

486 **Secondary Endpoints:** Liraglutide treatment effect on:

- 487 • Relative percent change from baseline in body weight
- 488 • Absolute change from baseline in body weight
- 489 • Absolute change from baseline in visceral adipose tissue mass
- 490 • Relative percent change from baseline in abdominal subcutaneous adipose tissue mass
- 491 • Absolute change from baseline in abdominal subcutaneous adipose tissue mass
- 492 • Change from baseline in VAT/SAT ratio
- 493 • Relative percent change from baseline in total fat mass
- 494 • Absolute change from baseline in total fat mass
- 495 • Relative percent change from baseline in fat-free mass
- 496 • Absolute change from baseline in fat-free mass

- 497 • Relative percent change from baseline in lower body adipose tissue mass
- 498 • Absolute change from baseline in lower body adipose tissue mass
- 499 • Change from baseline in total fat/fat-free mass ratio
- 500 • Relative percent change from baseline in hepatic fat content
- 501 • Absolute change from baseline in hepatic fat content
- 502 • Relative percent change from baseline in biomarkers of cardiometabolic risk
 - 503 - Markers of insulin resistance: fasting blood glucose, insulin, HOMA-IR
 - 504 - Markers of inflammation: CRP
 - 505 - Lipids: TG/HDL-C ratio
 - 506 - Natriuretic peptides: NT-proBNP
- 507 • Absolute change from baseline in biomarkers of cardiometabolic risk
- 508 • Change from baseline in heart rate and blood pressure
- 509 • Change in waist circumference

510

511 **TRIAL DESIGN AND METHODS:**

512

513 **Trial type:**

514 This is a randomized, double-blind, parallel-group, placebo controlled, prospective clinical trial to
 515 be conducted at a single center over 46 weeks (40 weeks on-treatment). There are two
 516 treatment arms. Patients will be randomized to liraglutide 3.0 administered once a day by
 517 subcutaneous injection or matching placebo, in addition to a reduced-calorie diet and increased
 518 physical activity. All participants will be prescribed a 500 kcal per day deficit diet, based on
 519 estimated 24-h energy expenditure.¹ All participants will be instructed to maintain physical
 520 activity at the recommended level of 150 minutes of moderate activity per week.

521

522 **Rationale for trial design:**

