 661 subgroup analyses by race, we will attempt to ensure Hispanics comprise at least 25% of the
 662 trial population. A pre-specified analysis stratified by those who did vs. did not lose $\geq 4\%$ body
 663 weight at 16 weeks of treatment will be performed prior to unblinding to determine differential
 664 outcomes among “responders” vs. “non-responders” as outlined in the package insert. All
 665 statistical tests are two-sided at a 5% significance level.
 666

667 **Interim Analysis:** No interim analysis will be performed.
 668

669 **Missing Data:** The preferred approach to missing data is to incorporate proactive standard
 670 operating procedures to mitigate the likelihood of missingness. We will implement measures to
 671 reduce missing data (both baseline and endpoint). The statistical analysis plan will describe
 672 analytical approaches to address missingness of data, including multiple imputation including
 673 the last observation carried forward (LOCF) and mixed-effects model repeated measure
 674 approaches. Sensitivity analyses will also be performed to determine the effect of missingness
 675 on the primary and secondary outcomes.
 676

DATA HANDLING AND RECORD KEEPING:

677 Subjects will be assigned an identification code. A subject's name and code will be contained
 678 within a small notebook and will be kept in a locked cabinet in the research coordinator's locked
 679 office. The research chart will contain personal health information and will be kept in locked file
 680 cabinet in the research coordinator's locked office. All other data on a computer will be de-
 681 identified with the subject's identification code. Blood samples waiting for analysis will not be
 682 labeled with the subject's name, but with the assigned identification code. The trial database will
 683 be password protected. No data will be sent over the internet unless it is encrypted. All email
 684 with subject-identifiable information will be password protected. Only key personnel will have
 685 access to the information in the trial database on an as-needed basis. Key personnel may not
 686

687 alter the data in the database or directly view all of it without specific cause and approval of the
688 PI.

689

690 **ETHICS:**

691

692 **Informed Consent**

693 Before screening takes place subjects will be provided with written and verbal information about

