1074 collected. Subjects will be advised with regards to the best possible post-trial treatment options
1075 for their weight management and metabolic syndrome. These treatments will be at the
1076 discretion of the local Investigator. Unblinding will occur at LPLV and after ascertainment of
1077 primary and secondary endpoints.

1078

1079

1080 **Premature discontinuation**

1081 If the trial subject opts for early trial termination, he/she will be asked to attend a premature trial
1082 discontinuation visit at the time of discontinuation. The purpose of this visit will be to assess
1083 body weight, occurrence of AEs and discuss end of trial imaging studies. The PI will offer end of
1084 trial imaging to assess for the primary and secondary efficacy endpoints if the subject has
1085 completed at least 40 weeks of trial treatment. Every effort will be made to assess for AE and
1086 SAEs during the trial for all patients including those prematurely withdrawing from the trial.

1087

1088 **TRIAL DRUGS AND MATERIALS:**

1089 Treatment with liraglutide or placebo will be blinded to the subjects and investigators throughout
1090 the trial.

1091

1092 **Trial medication(s) / devices(s)**

1093 The administration of liraglutide/ placebo will be as outlined above.

1094 The following trial products will be supplied by Novo Nordisk, Denmark.

- Liraglutide 6.0 mg/mL, 3 mL pen-injector for subcutaneous injection
- Placebo 3 mL pen-injector for subcutaneous injection

1095 Liraglutide will be available at a concentration of 6.0 mg/mL. Liraglutide and placebo will be
1096 supplied in a 3 mL pen-injector . Correct dosing is achieved by using the dose counter and the
1097 dose pointer to see how many mg to select. The subject will hear a "click" every time they turn
1098 the dose selector. The dose will not be set by counting the number of clicks the subject hears.
1099 Dosing with the liraglutide/ placebo pen-injector is controlled by turning the dose selector until
1100 the dose indicator shows the relevant dose (0.6, 1.2, 1.8, 2.4 or 3.0 mg, respectively or
1101 placebo). Therefore, the dose level (injection volume) of liraglutide or placebo is open labeled.

1102

1103

1104

1105

1106 Liraglutide or placebo is administered once daily by subcutaneous injections with the pen-
1107 injector, either in the abdomen, thigh or upper arm. Injections can be done at any time of day

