1167 temperature must be kept. Storage facilities will be checked frequently (at least once every
1168 working day).

1169
1170 No trial product(s) should be dispensed to any person not enrolled in the trial and the
1171 computerized randomization system should always be updated when dispensing trial product(s).
1172 Returned trial product(s) (partly used or unused including empty packaging material) must be
1173 stored separately from non-allocated trial product(s) until the monitor has performed drug
1174 accountability. The monitor will be responsible for retrieval of trial products from the site.
1175 Destruction of trial products will be done according to local laws and will be recorded on a
1176 Destruction Form, which will be signed by the person responsible for destruction, as agreed with
1177 the monitor.

1178
1179 **Randomization and Blinding**

1180 Trial participants and investigators will be blinded to treatment allocation throughout the trial.

1181

1182 **Randomization Scheme:**

1183 Participants will be randomly assigned using a computerized randomization code generated by
1184 UT Southwestern.

1185

1186 **Breaking of Blinded Codes**

1187 Blinding codes will be broken at the end of the trial. Blinding codes will only be broken before
1188 the end of trial if a subject develops a serious adverse event requiring knowledge of the
1189 treatment allocation. At such time, the subject will be considered to have completed the trial and
1190 will not undergo any further trial treatment but may be asked to undergo assessment of trial
1191 endpoints when feasible. Whenever a code is broken, the person breaking the code must print
1192 the Code Break Confirmation generated by the computerized randomization system, record the
1193 reason, and sign and date the document. If the subject should be withdrawn following a code
1194 break, a withdrawal session should be completed in the computerized randomization system.

1195

1196 **CONCOMITANT ILLNESSES AND MEDICATIONS**

1197 All concomitant illnesses and medications will be recorded in the CRF and assessed as AEs or
1198 not AEs. If a subject is prescribed a medication meeting criteria for withdrawal/exclusion, the
1199 subject will have the opportunity to decide whether to take such medication and withdraw from
1200 the trial or not take it and continue the trial.

SUBJECT SAFETY AND DATA MONITORING**ADVERSE EVENTS:****Definitions****Adverse Event (AE):**

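### The week-16 responder analysis is scheduled before unblinding; if run without the allocation, it cannot show whether early response relates to outcome on liraglutide, on placebo or on both

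*Protocol*

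**What the plan says.** The protocol's Statistical Methods section announces the analysis with "A pre-specified analysis stratified by those who did vs. did not lose" at least 4% of body weight, and continues: "weight at 16 weeks of treatment will be performed prior to unblinding to determine differential" outcomes among responders and non-responders. The responder rule is taken from the drug's labelling ("as outlined in the package insert"). Treatment arm is not named as a factor in that sentence.

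Two other sections fix when the allocation becomes known:

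- End of trial treatment strategy: "Unblinding will occur at LPLV and after ascertainment of" the primary and secondary endpoints.
- Breaking of Blinded Codes: "Blinding codes will be broken at the end of the trial", with earlier breaks only for individual serious adverse events.

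Two sections bear on who can be a responder:

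- Trial type: "All participants will be prescribed a 500 kcal per day deficit diet, based on" estimated energy expenditure. The activity advice likewise applies to both arms.
- The Liraglutide part of the background, after describing weight loss on the drug in three earlier trials: "These changes were significantly greater than weight loss seen in the placebo arms of these" trials. Placebo subjects therefore lose weight too, but less.

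**The concern.** The outcomes to be compared are measured at week 40, and the analysis is placed before the codes are opened. Taken literally, it falls where outcomes exist but the allocation does not. The only contrast then available is all responders against all non-responders.

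This has two consequences:

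1. **Arm of origin.** The rule comes from the label of the active drug, so the natural question is whether early response matters on liraglutide. A pooled gap has no placebo reference and cannot answer that.
2. **Arm mix.** If more liraglutide than placebo subjects reach 4%, responders contain more treated subjects. Part of the treatment effect then appears as a responder effect.

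This is not a detail left to the statistical analysis plan. The protocol itself fixes the timing, and an analysis plan that ran the analysis by arm after unblinding would depart from it.

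**Working it through.** **Inputs from the protocol (Sample Size Calculation).** Mean visceral fat reduction is 8% on placebo and 16% on liraglutide, SD 16, with 128 completers (64 per arm).

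**Check of the plan's own figure.** For a difference of 8 with SD 16, two-sided 5%, 64 per arm gives power 0.801 by the noncentral t, so 128 in total. With 28% dropout, 128/0.72 = 177.8, so 178. Both reproduce.

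**Assumed inputs (not in the protocol).** Week-16 weight change is normal with SD 5 points. Means for placebo/liraglutide are −3/−6 (case A) or −2/−6.5 (case B). The responder rate is p = Φ((−4 − mean)/5).

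| | Placebo rate | Liraglutide rate | Responders / non-responders |
|---|---|---|---|
| A | 0.421 | 0.655 | 69 / 59 |
| B | 0.345 | 0.691 | 66 / 62 |

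**Step 1. Arm mix with no link between weight and visceral fat within arm.** The pooled gap is 8 × [liraglutide share of responders − liraglutide share of non-responders].

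- A: shares 0.655/1.076 = 0.609 and 0.345/0.924 = 0.373; gap 8 × 0.236 = 1.9.
- B: shares 0.667 and 0.320; gap 8 × 0.347 = 2.8.

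With weight SD 4 to 6 the gap is 1.6 to 3.4. With rates set directly from 45%/55% to 25%/75% it is 0.8 to 4.0. The standard error of the pooled gap is 16 × √(1/69 + 1/59) = 2.8, and the same in B.

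**Step 2. Arm mix when weight and visceral fat are correlated within arm.** With correlation r and z = (−4 − mean)/5, the gap within an arm is 16·r·φ(z)/[p(1 − p)]. For case A, r = 0.3:

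- Placebo: 16 × 0.3 × 0.391/(0.421 × 0.579) = 7.7.
- Liraglutide: 16 × 0.3 × 0.368/(0.655 × 0.345) = 7.8.

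| Case, r | Gap on liraglutide | Gap on placebo | Pooled gap | Pooled minus within-arm |
|---|---|---|---|---|
| A, 0.3 | 7.8 | 7.7 | 9.2 | 1.4 to 1.5 |
| A, 0.5 | 13.0 | 12.8 | 14.1 | 1.1 to 1.3 |
| A, 0.7 | 18.3 | 18.0 | 19.0 | 0.7 to 1.0 |
| B, 0.3 | 7.9 | 7.8 | 9.7 | 1.8 to 1.9 |
| B, 0.5 | 13.2 | 13.0 | 14.3 | 1.1 to 1.3 |
| B, 0.7 | 18.5 | 18.3 | 18.9 | 0.5 to 0.7 |

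The net excess is about 0.5 to 1.9 points, below the standard error of 2.8.

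**Step 3. Can the pooled result show the arm of origin?** Keep the arm means at 8 and 16. With gap g in an arm, responders average the arm mean + (1 − p)g and non-responders the arm mean − p·g.

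| True gap (liraglutide, placebo) | Pooled, A | Pooled, B |
|---|---|---|
| 8, 0 | 5.5 | 6.2 |
| 0, 8 | 5.8 | 6.4 |
| 4, 4 | 5.7 | 6.3 |

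These three patterns differ by at most 0.3 points when pooled. They are illustrations; nothing in the protocol suggests any one of them.

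**Step 4. What the by-arm analysis can deliver.** The standard error of the gap within an arm is 16 × √(1/(64p) + 1/(64(1 − p))). In A this is 4.2 (liraglutide) and 4.1 (placebo); in B it is 4.3 and 4.2. For the difference between the two gaps it is 5.8 or 6.0.

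**Step 5. The arm comparison inside strata.** If liraglutide improves every subject by 8 points, the difference between arms within responders or within non-responders reads between 1.5 and 6.2 points for r = 0.3 to 0.7. Response is itself changed by treatment, so subjects in the same stratum of the two arms are no longer alike.

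**The case against.** The strongest reply is that performing an analysis before unblinding need not mean performing it without the allocation. The blind is stated for participants and investigators. The Visit 3 section has randomization implemented by an independent party at the university, who could hold the codes. A run by that party, or on masked arm codes, would respect the sentence and pool nothing. In its context, after a comparison between groups and a list of subgroups, a stratified analysis may well mean comparing the arms within each response stratum. The sentence may also be loose drafting for fixing the definition before unblinding. All of this stands as a possible reading. The sentence nevertheless says that the analysis is performed at that point, and the protocol describes no masked codes and no analyst with the allocation. It should state which is meant.

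Two stronger readings are tempting, and the protocol does not support them:

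- **That pooling creates a large false responder effect.** The 1.9 or 2.8 points require no relation between early weight loss and visceral fat change within arm. With a moderate relation the excess shrinks to about 0.5 to 1.9 points beside within-arm gaps of about 8 to 18. All of these figures rest on assumed responder rates.
- **That the arm information is lost for good.** Nothing forbids repeating the analysis by arm once the codes are open. Weight is recorded through the treatment visits and outcomes at week 40.

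It is also fair that a by-arm analysis is imprecise, and that the 4% threshold on measured weight is already fixed, so responder status needs no further definition.

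**Conclusion.** The point holds in a limited form. The protocol places the responder outcome analysis before unblinding and describes no means of using the allocation at that stage. If it is run without the allocation, it cannot show whether early response relates to outcome on liraglutide, on placebo or on both. That part does not depend on exact responder rates.

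The added arm mix is secondary, conditional on the assumed rates and correlations, and no larger than about one standard error in the two main cases. If masked codes or an independent analyst are intended, this is a wording error only. It is a minor matter in one secondary analysis. A reader might infer that the trial's main result is at risk; it is not, because the primary intention-to-treat comparison does not use response status or this timing.

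**What to change.** In Statistical Methods, change the timing clause so that the analysis is *specified before unblinding and performed with the treatment allocation after unblinding*. This keeps the protection of pre-specification.

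Report week-40 outcomes by week-16 response within each arm, side by side, labelled descriptive. Label any comparison of arms inside a response stratum as non-randomised, because response is a post-randomisation variable affected by treatment. If a run on masked codes or by an independent holder of the allocation is what was meant, say so instead.

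The cost is one or two sentences in the protocol and the analysis plan, with no extra data. The downside is imprecision: a standard error of about 4 points for each within-arm gap and about 6 for their difference, with no causal claim about responders.
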